To establish the feasibility of completing the Catherine Bergego Scale (neglect) (Azouvi et al., 1996), Scale for Contraversive Pushing (SCP) (Karnath et al., 2002) and bucket test (SVV) (Zwergal et al., 2009) in a clinical environment with acute stroke patients to assist with identification of vertical perception loss.

The secondary research questions that this study will aim to address are:

- What percentage of patients admitted to an acute stroke unit show a positive test for vertical perception loss within four weeks of admission (evidence of subjective visual vertical (SVV) tilt on either bucket test or Catherine Bergego Scale or evidence of subjective postural vertical (SPV) tilt on SCP)
- For those able to complete the assessments, does vertical perception loss show any relationship with:
 - Discharge (DC) destination
 - Care package size on discharge
 - Number of inpatient falls
 - Level of functional independence on discharge
- Is there a trend for any element of the SCP or the Catherine Bergego to be more correlated with SVV tilt.

2. Objectives and outcome measures.

Primary objective:

To establish the feasibility of completing the Catherine Bergego Scale, the Scale for Contraversive Pushing (SCP) and the bucket test in a clinical environment with acute stroke patients, to assist with identification of vertical perception loss.

Primary outcomes:

The primary outcome is to understand the feasibility of completing the suite of outcome measures in an acute stroke setting:

- Proportion (%) of patients on whom the assessments are attempted.
- Percentage of patients who are able to complete all three assessments within four weeks of admission.
- Time taken to complete the three measures in an acute clinical setting
- A recommendation regarding the most feasible time point to complete these assessments.

Secondary outputs:

The secondary aims are to gain a further understanding of vertical perception loss in acute stroke patients.

- An understanding of factors that prevent or facilitate completion of these three assessments
- An understanding of healthcare professionals' experiences of completing these assessments in an acute stroke unit.
- An understanding of whether people with stroke (or their advocates) find it appropriate to complete all three assessments in an acute stroke setting.
- Percentage of patients admitted to an acute stroke unit showing a positive test for vertical perception loss within four weeks of admission.

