Participants will only be enrolled in the research if an advocate can be found to consent on their behalf. If someone lacks capacity and does not have an advocate they will be ineligible for inclusion in the research. Advocates will be identified through the medical records of the potential participant and will usually be their next of kin or other named contact. They will only be able to consent once they have read a PIS and had time to ask questions of the research team.

On reading the PIS if the patient or their advocate is willing to participate then they will be asked to sign a consent form, by the research team or chief investigator. Potential participants will have a minimum of 12 hours to read the PIS.

If a participant who lacked capacity, and was consented by an advocate, regains capacity then their informed consent to continue will be sought.

Study protocol

For those patients who consent, the qualified physiotherapists or occupational therapists on the stroke unit, will then attempt to complete all 3 outcome measures with the patient (see assessors and outcome measures below). If the patient is unable to complete any elements of the outcome measure for any reason, this will be recorded. If the patient is unable to complete the outcome measures, then an attempt will be made to complete the outcome measures at 1 week post

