admission, if still unable they will be attempted again at 2 weeks and 4 weeks post admission. At the point participants complete all 3 outcome measures or at 4 weeks (whichever is earliest) most will have no further active participation in the quantitative part of the study. The assessments do not need to all be completed in one sitting and can be spread across sessions. If a patient is unable to be consented at 48 hours they will be consented as soon after this point as possible up to one week after admission, and this will be recorded. If patients are discharged or have a change in status following consenting to participate but prior to completion of the outcome measures any data collected to date will be utilised in the study results and the reasons for non-completion of the outcome measures will be noted as this will inform the feasibility of these outcome measures. The length of time taken to complete the measures will be recorded by the administrator. The expectation is that administration of all three outcome measures will take no longer than one hour. Due to the observational nature of the SCP and Catherine Bergego Scale elements of these can be completed during therapy sessions. The results and implications of the results of the outcome measures will be discussed with the patient or their advocate should they wish. The impact of the results on the therapists will be explored in a focus group.

At the point the participants are discharged from the stroke unit (this could include but not be restricted to: transfer to another rehabilitation facility, to undergo further neurological observation or intervention, discharge home, to undergo further unrelated medical interventions) their notes will be accessed and the following data extracted:

- Demographic details (age, gender)
- Type and location of stroke
- NIHSS on admission
- Number of in-patient falls
- Discharge (DC) destination
- Level of care required on DC – either care home or size of care package
- Functional ability on DC using the Modified Rankin Scale (MRS) (van Swieten et al., 1988) and the Barthel Index (Mahoney and Barthel, 1965) as these are routinely collected for all patients
- Amount of physiotherapy and occupational therapy received during inpatient stay as submitted to the Sentinel Stroke National Audit Programme (SSNAP). This includes minutes of therapy received per session of therapy, number of sessions of therapy per day and number of days on which therapy was received

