will be calculated. Demographic data of the participants will be tabulated for display including: number of patients with left or right stroke, number of patients with haemorrhage or infarct stroke, female/male/non-binary/other gender, mean length of stay, location of stroke, median NIHSS on admission, median MRS and Barthel Index on discharge, place of discharge (home/care home/other), care needs on discharge (nil, one, two, three or four calls per day or 24 hour and number of carers required), number of in-patient falls, median minutes of therapy per day (for OT and Physiotherapy) and median number of days on which OT and Physiotherapy were received.

The main outcome will be the percentage of consenting patients who are able to complete the three outcome measures within four weeks of admission. The percentage of patients able to complete each of the outcome measures individually will be calculated to see if one of the outcome measures is more feasible than the others. Reasons for non-completion will be collated for each of the outcome measures and presented using an appropriate tool. The mean time and standard deviation (SD) to complete all three and each individual outcome measure will be presented. To identify the most feasible time point to complete the outcome measures median (and confidence intervals) time to completion of each outcome measure and time to completion of all three outcome measures will be calculated. The percentage of participants completing each or all of the measures at 48 hours, 1 week, 2 weeks and 4 weeks will be presented.

The median scores and confidence intervals for the SCP and Catherine Bergego scale will be calculated, as well as the mean and SD for the bucket test. The percentage of patients with vertical perception loss will be reported – this will be defined as a positive test on one or more of the measures (SVV >2.5°, Catherine Bergego Scale >1, SCP >0.5). For each patient it will be noted if they test positive on one, two or all three measures. This will assist in informing which of the measures will be required in future studies.

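### Retry-until-complete testing makes the percentages at 48 hours, 1, 2 and 4 weeks non-comparable, so neither they nor the median time to completion show which time point is most feasible

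*Combined protocol and SAP*

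**What the plan says.** The Trial Summary and Section 2 list among the primary outcomes: "A recommendation regarding the most feasible time point to complete these assessments".

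Section 6 (Study protocol) sets the testing schedule. All three measures are attempted after consent. Then: "If the patient is unable to complete the outcome measures, then an attempt will be made to complete the outcome measures at 1 week post" (counted from admission). Later attempts follow the same rule: "if still unable they will be attempted again at 2 weeks and 4 weeks post admission". Completers leave the schedule: "At the point participants complete all 3 outcome measures or at 4 weeks (whichever is earliest) most will have no further active participation". That sentence concerns the quantitative work only. The exception is a re-test at discharge in about one third of each severity group.

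First attempts do not all fall at the same time. Under Recruitment, patients are approached from 48 hours to one week after admission, and "Potential participants will have a minimum of 12 hours to read the PIS". The Study protocol adds: "If a patient is unable to be consented at 48 hours they will be consented as soon after this point as possible", with one week after admission as the limit.

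Section 8 names two statistics. The first carries the purpose: "To identify the most feasible time point to complete the outcome measures median (and confidence intervals) time to completion of each outcome measure", and of all three together, will be calculated. The second follows it: "The percentage of participants completing each or all of the measures at 48 hours, 1 week, 2 weeks and 4 weeks will be presented".

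The plan does not give the denominator for these percentages or say whether they are cumulative. It does not say how patients discharged before completing enter them, or what rule turns them into a recommendation.

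**The concern.** The patients behind each percentage differ. Everyone who consents gets a first attempt. At 2 and 4 weeks the only patients tried are those who have not yet completed. At 1 week the group combines retries with first attempts in patients who consented late. Time since admission is therefore mixed up with previous failure and, at 1 week, with timing of consent.

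Each reading of the percentages inherits this:

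- **Completed at this time point:** later rows shrink because completers have left.
- **Success among those attempted:** later rows hold the harder cases.
- **Cumulative:** rows can only rise, so 4 weeks is never lower than any other.

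The median time to completion comes from the same schedule. At stake is one of the four primary outcomes: a recommendation based on comparing the rows could name the wrong time point.

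**Working it through.** The plan gives no expected completion rate, so there is no figure of its own to reproduce. The schedule below is from Section 6. All rates are assumptions chosen to show how the statistics behave.

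**1. Time has no effect.** With a constant chance *p* at each attempt, the share first completing at attempt *k* is p(1−p)^(k−1).

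| p | First completing at attempts 1 to 4 (%) | Cumulative (%) |
|---|---|---|
| 0.3 | 30 / 21 / 14.7 / 10.3 | 30 / 51 / 65.7 / 76.0 |
| 0.5 | 50 / 25 / 12.5 / 6.3 | 50 / 75 / 87.5 / 93.8 |
| 0.7 | 70 / 21 / 6.3 / 1.9 | 70 / 91 / 97.3 / 99.2 |

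All four times are equally feasible, yet the non-cumulative rows fall and the cumulative rows rise. The median is reached at the second attempt for p = 0.3 (51%) and at the first for p = 0.7 (70%). It moves with the overall success rate although no time point is better than another.

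**2. Patients differ in ability.** A simulation of 400,000 patients used a patient-level logit of success with mean 0 and SD 1.5, a fixed increment per attempt, and retries only after failure.

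| Increment | True average feasibility (%) | First completing (%) | Success among attempted (%) | Cumulative at 4 weeks (%) |
|---|---|---|---|---|
| 0 | 50 / 50 / 50 / 50 | 50 / 18 / 9 / 5 | 50 / 35 / 27 / 23 | 82 |
| 0.5 | 50 / 59 / 67 / 75 | 50 / 22 / 12 / 7 | 50 / 45 / 44 / 45 | 91 |

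Constant and improving feasibility give the same ordering of the first-completion rows.

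**3. Ability, once gained, lasts.** Let a_k be the share able at visit k, assumed 50 / 65 / 75 / 80%, with nobody discharged.

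- First completions, a_k − a_(k−1): 50 / 15 / 10 / 5%.
- Success among attempted, (a_k − a_(k−1)) / (1 − a_(k−1)): 50%, 15/50 = 30%, 10/35 = 28.6%, 5/25 = 20%.
- Cumulative: 50 / 65 / 75 / 80%.

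The first two rank the time points in reverse of the truth. The cumulative curve equals it.

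**4. Add discharge.** Let s_k be the share still on the unit, assumed 100 / 70 / 45 / 20% and unrelated to ability.

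- First completions, s_k(a_k − a_(k−1)): 50 / 10.5 / 4.5 / 1%.
- Cumulative: 50 / 60.5 / 65 / 66%.
- Result if everyone present were tested at that visit, s_k × a_k: 50 / 45.5 / 33.8 / 16%.

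The cumulative figure is highest at 4 weeks, although testing everyone present then would yield completion in 16% of those who consented.

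**5. Add late consent.** Approach from 48 hours plus at least 12 hours' reading gives 60 hours at the earliest, so few first attempts can fall at 48 hours. Suppose half of patients have their first attempt at 1 week, with step 4 otherwise unchanged. In percent of all who consented:

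- Retries at 1 week: tested 0.5 × 0.70 × 0.50 = 17.5; completing 0.5 × 0.70 × 0.15 = 5.25, or 30% of those tested.
- First attempts at 1 week: tested 0.5 × 0.70 = 35; completing 35 × 0.65 = 22.75, or 65% of those tested.
- Combined: 28 / 52.5 = 53.3%.

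The non-cumulative rows become 25 / 28 / 4.5 / 1%. The 1-week figure is a blend of two different rates.

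**6. Where the ranking survives.** Using the model in step 2:

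- Mean −2, increment 1: true feasibility 19 / 33 / 50 / 67%; first completions 19 / 22 / 22 / 18%; success among attempted 19 / 27 / 37 / 48%.
- Mean 0, increment 1: true feasibility 50 / 67 / 81 / 90%; success among attempted 50 / 54 / 61 / 68%.

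In both, success among attempted has the right order but understates the later times: 48% against 67%, and 68% against 90%, at the last attempt.

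**The case against.** The best defence has four parts.

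- **The percentages are only presented.** Section 8 attaches its stated purpose to the median, and no passage plans a comparison of row heights. This is true. But the median comes from the same retry schedule (step 1), so moving the weight to it does not help.
- **The cumulative reading is sound.** Read as completed by a given time, the percentages are points on a useful curve. With lasting ability and no discharge they equal the true ability at each time (step 3). This stands, and the fix is built on it. What the plan lacks is the label, the denominator, the handling of discharge, and wording that limits the conclusion to what the curve shows.
- **Other evidence exists.** Reasons for non-completion, the therapist focus groups and the patient survey can inform a judgement, and Section 8 bases the overall feasibility decision on collated results. They add context but do not remove the selection. The discharge re-test covers about a third of each severity group and has no fixed time, so it does not fill the gap.
- **Some 1-week patients are first attempts.** Correct. A reader might infer that every attempt after the first opportunity is in patients who had already failed. Section 6 does not support that at 1 week, because consent may come up to one week after admission. It does hold at 2 and 4 weeks.

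A reader might also infer that the first attempt must always look best, so that the retry rule alone fixes the answer. The documents do not support this: they give no completion rates, and the ranking depends on them. Step 6 gives rows of 19 / 22 / 22 / 18%. With lasting ability of 20 / 70 / 80 / 85%, first completions are 20 / 50 / 10 / 5%.

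**Conclusion.** The concern holds in a bounded form. The percentages at the four time points are not comparable measures of feasibility at each time. Non-cumulative rows and success among those attempted are biased against later time points, by an amount that depends on the true rates. Cumulative rows can only rise. The median reflects when patients first succeed under this schedule. Neither planned statistic shows which time point is most feasible, although the cumulative curve does show by when the measures are completed.

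On size, average feasibility of 50% throughout can produce rows of 50 / 18 / 9 / 5%, and lasting ability rising from 50 to 80% can produce 50 / 15 / 10 / 5%. These figures rest on assumed rates and on discharge being unrelated to ability. The direction of the bias comes from the schedule in Section 6. It would be too strong to say that the data cannot inform timing at all. The data remain usable and safety is not affected, but one primary outcome cannot be answered as Section 8 is written, so the section should be changed.

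**What to change.** In Section 8:

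1. For each scheduled attempt, report the number still on the unit, the number attempted (first attempts and retries separately) and the number completing. Label retry results as success in previously unsuccessful patients.
2. Replace the unlabelled percentages with the cumulative incidence of completion by days since admission among all consenting patients. Treat discharge or death before completion as a competing event.
3. Base the recommendation on that curve, worded as the time by which the measures are completed under this retry schedule. Do not infer the most feasible time point by comparing percentages across time points.

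Modelling first attempts by day would not be a substitute. Consent closes at one week, so such a model carries essentially no information on 2 and 4 weeks, and the timing of consent may itself reflect capacity or whether an advocate could be found.

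The cost is slightly more analysis, the date and outcome of each attempt on the data form, and a narrower conclusion. Patients need no extra testing.

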	Patients with pre-morbid visual impairment that will not allow them to see the bucket test. Glasses can be worn.
	Inability to speak the English language and no interpreter can be found

6. Trial Procedures

Recruitment

All patients admitted to an acute stroke unit, who meet the inclusion criteria, may be invited to participate. Potential participants will be identified during the daily handover by members of the clinical or research team. Those meeting the inclusion criteria will be approached by a member of the research or clinical team and invited to participate. This will take place between 48 hours and one week after admission. Potential participants will be provided with the participant information sheet (PIS) regarding this study. If the patient is unable to consent due to cognitive or language impairment or low level of consciousness then their advocate will be approached. Where possible potential participants will be supported to consent using information in different formats (e.g.

through use of pictures) or the skill of appropriate members of the clinical team (e.g. speech and language therapists).

The number of people admitted to hospital with stroke who have language or cognitive impairments that may prevent them being able to consent is substantial. To exclude these potential participants would significantly impact the validity and generalisability of the results. Especially as those with significant strokes are more likely to present with vertical perception loss as well as cognitive and language impairment. If they were excluded a large number of patients with vertical perception loss may not be identified. These groups are often underrepresented in stroke research. If someone is unable to consent an advocate will be approached to consent on their behalf.

Those taking consent will decide on capacity. This includes the chief investigator and the stroke research nurse. Both have significant experience working with people with stroke. Both have undergone Good Clinical Practice training and Mental Capacity Act Training. If in any doubt about capacity other members of the healthcare team (e.g., Speech and Language Therapists) can give advice as to whether the potential participant has capacity or whether their advocate should be approached.

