The participant information sheet will make it clear that there is no obligation to participate and that it will not impact their future care. Participants will have the right to withdraw from the study at any point until the time of discharge without detriment and any data already collected up to the point of withdrawal will be utilised in the results.

Confidentiality

All data will be fully anonymised and no participant will be identifiable in any resulting outputs from this research. Data will be stored on a NHS computer or required platforms and anonymised data will be stored on a University of Winchester password protected OneDrive behind a two factor authentication. General Data and Protection Regulations (GDPR) will be followed at all times.

Participants of the focus groups will have the right to withdraw up to the point at which the focus group has been transcribed (10 days after the focus group). At this point the original recording will be deleted, the participants anonymised and withdrawal will not be possible. Anonymised data will be shared with the researcher's supervisory team.

Additional Ethical considerations

All participants will be given information on how to seek support or who to contact to ask questions regarding the research.

If a participant loses capacity during the study any data collected to date will be anonymised and used in the results but no further data would be collected, unless they regain capacity. This is made clear in the participant information sheet and can be discussed with the participant prior to them consenting.

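### The any-of-three definition of vertical perception loss has no denominator and no class for patients with a missing test and no positive result, so the reported percentage depends on how many tests were done and on an unstated rule

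*Combined protocol and SAP*

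**What the plan says.** Section 8 (Statistics and Data Analysis) says of vertical perception loss that "this will be defined as a positive test on one or more of the measures", with cut-offs of SVV above 2.5°, Catherine Bergego Scale above 1 and SCP above 0.5. It adds a count per patient: "For each patient it will be noted if they test positive on one, two or all three measures". That count is meant to help decide which measures later studies need.

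Incomplete batteries stay in the data. For patients who are discharged or change status before finishing, section 6 (Study protocol) says "any data collected to date will be utilised in the study results and the reasons for non-completion of the outcome measures will be noted". Section 10 says the same after withdrawal ("any data already collected up to the point of withdrawal will be utilised in the results") and after loss of capacity ("If a participant loses capacity during the study any data collected to date will be anonymised and used in the results").

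The secondary research question at the end of section 1 asks for the percentage among patients admitted to the unit. Only the next question, on discharge outcomes, is limited to those able to complete the assessments. No section gives the denominator of the percentage or says how to classify a patient with a missing test and no positive result. None plans a breakdown by number of tests done.

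**The concern.** Under an any-of-three rule, one positive result settles that a patient has loss. The absence of loss is settled only by three negative results. A patient who is negative on one or two tests and missing the rest is undetermined, and the plan has no such class.

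This matters here because the main outcome in section 8 is the percentage of consenting patients who can finish all three tests, so incomplete batteries are part of what is being studied. Section 1 also says that measuring visual vertical alone may miss some patients with loss, so a missing test can hide a positive patient.

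Two results are exposed. One is the percentage with loss, a named secondary outcome. The other is the positive-test tally: a patient who did two tests cannot score three, so a test that many patients cannot do will appear to identify fewer cases.

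**Working it through.** **Plan's own figure.** There is none to reproduce. The documents state no expected completion rate, per-test positivity, prevalence or precision. Every rate below is an assumption.

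**Direction under the literal rule.** The tests done are a subset of the three, so P(any observed test positive) ≤ P(any of three positive). Counting a missing test as not positive can only equal or lower the full-battery percentage.

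**Size under the literal rule.** Assume each test is positive in 30% of patients, with normal latent variables cut at the 70th percentile and pairwise correlation ρ. Let P1, P2 and P3 be the chance of any positive with one, two or three tests.

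| ρ | P1 | P2 | P3 |
|---|---|---|---|
| 0.3 | 0.300 | 0.472 | 0.582 |
| 0.5 | 0.300 | 0.443 | 0.530 |
| 0.7 | 0.300 | 0.409 | 0.473 |

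If a fraction f is incomplete at random, the shortfall in the study percentage is f × (P3 − P2) with one test missing and f × (P3 − P1) with two missing. With f = 0.30:

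- One missing: 0.30 × (0.582 − 0.472) = 3.3 points at ρ = 0.3, and 0.30 × (0.473 − 0.409) = 1.9 points at ρ = 0.7.
- Two missing: 0.30 × (0.582 − 0.300) = 8.5 points at ρ = 0.3, and 0.30 × (0.473 − 0.300) = 5.2 points at ρ = 0.7.

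With f = 0.10 each figure is one third as large: about 0.6 to 1.1 points with one missing and 1.7 to 2.8 with two.

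**Other handlings.** A simulation of 1,000,000 patients per scenario used per-test positivity of 20% or 40%, latent correlation 0 or 0.5, 10%, 30% or 50% incomplete, and one or two tests missing. Incompleteness was either unrelated to the latent severity behind the tests or correlated 0.6 with it. Three rules were compared with the full three-test percentage:

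- A, everyone kept and a missing test counted as not positive (the literal rule): low in every scenario, by 0.6 to 3.9 points with 10% incomplete, 2.3 to 11.5 with 30% and 3.7 to 19.3 with 50%.
- B, complete batteries only: unbiased when incompleteness was unrelated to severity, about 3 to 15 points low when it was related as assumed.
- C, incomplete patients dropped only if they had no positive: from −0.7 to +14.6 points, mostly upward.

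One scenario in full (20% positivity, correlation 0.5, 30% incomplete, two tests missing):

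| Incompleteness | Full | A | B | C | Bounds |
|---|---|---|---|---|---|
| Unrelated to severity | 38.9% | 33.2% | 38.9% | 43.7% | 33.2% to 57.2% |
| Related to severity | 38.9% | 31.0% | 29.1% | 38.5% | 31.0% to 50.4% |

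**Same data, different rules.** Take 50 invented patients: 35 complete (18 positive) and 15 partial (6 positive, 9 undetermined).

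- A: (18 + 6)/50 = 48%.
- B: 18/35 = 51%.
- C: 24/(50 − 9) = 24/41 = 59%.
- All undetermined counted as positive: (24 + 9)/50 = 66%.

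The 48% to 66% span shows what is unresolved in such data. It is not an estimate of bias.

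**The case against.** The strongest reply is that the plan fixes no direction. A reader might infer that the percentage will be too low, or that every handling biases it. The documents do not support either inference. With no stated denominator, the downward direction holds only on the literal reading, rule C usually goes the other way, and complete batteries alone are unbiased if incompleteness is unrelated to loss. This stands.

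A reader might also infer that the protocol expects the most affected patients to be untestable. Section 6 (Recruitment) does say that "those with significant strokes are more likely to present with vertical perception loss as well as cognitive and language impairment", but as an argument for advocate consent. It does not say that these impairments prevent testing. Two of the measures are observational and can be filled in during therapy, and the bucket test accepts a raised hand. Early discharge could equally remove milder patients. A link between incompleteness and loss is plausible but is an inference.

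The outcome can also be read as observed yield, since sections 1 and 2 speak of patients showing a positive test. On that reading, positives over all patients is the intended quantity. Section 8 speaks instead of patients with vertical perception loss, so the target itself needs stating.

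Repeat attempts at 1, 2 and 4 weeks, per-test completion rates and reasons for non-completion will reduce and reveal the missing data. They do not supply a classification rule.

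**Conclusion.** The point holds as a gap with consequences. The stated rule, applied literally to partial batteries, counts undetermined patients as not having loss, so the percentage is at or below the full-battery figure and the tally is capped by the number of tests done. Under the assumptions of 30% positivity, correlation 0.3 to 0.7 and 30% incomplete at random, the shortfall is about 2 to 3 points with one test missing and 5 to 8 with two. The true size is unknown because the documents give no rates, and under other handlings the direction changes.

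'Low' here means relative to the same composite with all three tests done. An any-of-three rule may also add false positives, so nothing follows about error against true loss. This is a descriptive secondary outcome with no hypothesis test or numeric progression rule attached. The change is a worthwhile, inexpensive improvement, and the omission does not threaten the study's main feasibility result.

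**What to change.** In section 8, take as denominator the consenting patients with at least one of the three tests completed, and report those with none separately. Then:

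1. Classify each patient as loss (any positive), no loss (all three done and all negative) or undetermined (no positive and at least one test missing).
2. Report the percentage with loss as two bounds on that denominator, with undetermined patients counted first as negative and then as positive, each with a 95% confidence interval.
3. Beside the bounds, give the complete-battery percentage and each test's own positive percentage with its own denominator.
4. Show the tally of one, two or three positives for complete batteries only, and list partial batteries by which test was missing.

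The cost is a few sentences of analysis text and one extra table, with no new data collection. The drawback is a range in place of a single headline percentage.
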